1 BACKGROUND AND RATIONALE

As a global public health priority, there has been a pressing demand for the development and deployment of novel interventions to prevent and delay the onset of dementia. In recent years, Computerized Cognitive training (CCT) has garnered considerable evidence in improving the cognitive outcomes of individuals living with Mild Cognitive Impairment (MCI), a transitional stage between normal aging and dementia. The aim of this pilot study is to assess the feasibility and efficacy of CCT, specifically a multi-domain Virtual Reality Cognitive Training (VRCT) program on the cognition of individuals with MCI. The VRCT program will be conducted weekly over a period of 10 weeks for participants aged 65-85 with a diagnosis of MCI. 30 participants will be recruited from specialist outpatient clinics and they will be randomized into either the VRCT intervention group or the active control group. All participants will be assessed at baseline and post-intervention. We hypothesize favorable acceptability of the VRCT program. We also postulate positive changes on neuropsychological measures of attention, processing speed, memory and executive function following program completion. We expect these gains in cognition to be translated to improvements on secondary outcomes including mood and self-reported everyday memory functioning. In CGH, there is currently a lack of follow-up intervention options for patients who have received a diagnosis of MCI. Usual care procedures would include medication for risk factors as well as health advice for lifestyle factors such as exercise, diet and cognitively stimulating activities. If outcomes from this study prove to be positive, it will add to the evidence base of the novel application of Virtual Reality technology to Cognitive Training in a clinical setting. Furthermore, this will provide clinicians in CGH with an innovative intervention option to meet the needs of MCI patients in maintaining and enhancing their cognitive functions.

1.1 General Introduction

Over the last four decades, global prevalence of dementia has increased exponentially, with regions including Latin America, North Africa and Southeast Asia having a proportionately higher acceleration in prevalence as compared to other world regions¹. As one of the leading causes of disability and dependency in old age, dementia poses tremendous socioeconomic impacts to healthcare systems worldwide, with medical, social care and informal care costs estimated at US\$604 billion annually². In Singapore, the population of older adults has also seen dramatic growth: from 2.5% of the population in 1965 to 13.7% in 2018³. This has brought about an increase in the number of people diagnosed with dementia, currently found to be at 10% for older adults aged 60 and above⁴.

1.2 Rationale and Justification for the Study

Mild cognitive impairment (MCI) is a symptomatic transitional stage between normal aging and dementia, where individuals display objective evidence of cognitive impairment but still maintain functional and social independence⁵. An estimated 10% to 55% of MCI cases progress into dementia over a 2- to 6-year time period⁶. Given the disability and distress associated with worsening cognition, growing efforts have been made to prevent or delay the progression of MCI to dementia. With an absence of approved pharmacological options to treat the underlying pathophysiological mechanisms of MCI, increasing attention has been placed on lifestyle modifiable factors and non-pharmacological interventions to target the cognitive symptoms⁸.

A non-pharmacological intervention that has garnered interest and considerable evidence in recent years is Computerized Cognitive Training (CCT). CCT involves guided repetitive practice of standardized

tasks designed to target specific cognitive skills or processes, with the aim of improving cognition via reinforcement of neural pathways⁹. Accessibility to cognitive training is enhanced with the use of technology, particularly for older adults whose mobility may be limited. The computerized features also enable a more individualized approach where activities may be tailored to the users' ability levels, thereby improving user engagement. The efficacy of CCT has been rigorously reviewed in recent meta-analyses of randomized control trials which reported cognitive benefits in both cognitively healthy older adults and patients with mild cognitive impairment^{10,11}. Notably, the overall effect size of CCT on cognition was found to be higher for individuals with MCI ($g = 0.35$) as compared to individuals with dementia ($g = 0.28$)¹¹ as well as healthy older adults ($g = 0.22$)¹⁰, indicating the use of CCT as a viable intervention for enhancing cognition in people with MCI.

1.2.1 Rationale for the Study Purpose

Among the various types of CCT interfaces that are currently available, including computer/tablet-based programs and videogames, Virtual Reality (VR) technology is the most recent and novel application of CCT. As compared to its traditional counterparts, the wrap-around display screens of VR systems offer the added advantage of a simulating and immersive environment that produces a sensation of "presence" or "being there". VR systems also afford a versatile experimental platform that can provide timely feedback to clinicians regarding patient progress via real-time monitoring of the system performance¹². Evidence for the efficacy of VR on health-related outcomes has been demonstrated in other clinical populations including cognitive rehabilitation for patients of traumatic brain injury¹³ and exposure therapy for patients with anxiety and phobic disorders¹⁴. While the evidence base for VR application on MCI patients is currently still limited, available research suggests its utility in enhancing treatment adherence and cognitive outcomes of MCI patients. In a study examining the effects of an attentional task on selective and sustained attention, participants with MCI were exposed to two task conditions – a highly realistic image-based rendered VR condition and a paper version of the task. Not only did participants endorse a preference for the VR interface over the paper condition, apathetic participants reported greater preference for the VR condition than non-apathetic participants, indicating VR's potential in improving adherence to cognitive training¹⁵. One study had developed a 6 months VR memory training (inclusive of 3 months training phase and 3 months booster phase) for nursing home residents with memory deficits¹⁶. The authors found significant improvement in memory test scores, especially in long-term recall, for participants in the intervention group whereas those in the control group demonstrated progressive decline in their memory functions¹⁶. These positive results in the memory domain are supported by another study which examined the efficacy of memory and balance training VR program on participants with MCI¹⁷. Finally, even among MCI participants of Chinese ethnicity, VR seems to be acceptable and efficacious, with the VR group showing greater improvement in objective memory performance post-training than the non-VR group¹⁸.

While other VR programs have largely focused on a single cognitive domain, we aim to assess the effects of a broad-based VRCT program that targets multiple cognitive outcomes. As compared to single-domain CT intervention, multi-domain CT appeared to be more advantageous in maintaining treatment effects¹⁹. Notably, two high quality randomized controlled trials have demonstrated interesting neuroimaging outcomes where increases in hippocampal functional connectivity were observed following multi-domain CCT, which is postulated to prevent memory loss²⁰. To our knowledge, this research would be the first of its kind in Singapore, thereby contributing to the current evidence base on the efficacy of VRCT on enhancing the cognition of individuals with MCI. In the clinical setting, MCI patients in Changi General Hospital are offered a limited range of treatment and follow-up options after receiving their diagnosis due a lack of available interventions. Through this pilot feasibility study, we hope to introduce an innovative clinical service to target the cognitive health of our patients with MCI. We believe that the current feasibility study will provide us with useful information

in guiding us to conduct a randomized controlled trial for a VRCT group program as well as a longitudinal study in the future to evaluate the effects of VRCT in delaying the progression of MCI to dementia. We hope that this novel intervention will improve our clinical service, efficiency and reduce manpower needed to run cognitive interventions for our patients.

1.2.2 Rationale for Study Design

This is a pilot feasibility study using a parallel design where participants are randomized into either the Virtual Reality Cognitive Training (VRCT) intervention group or the active control group.

2 HYPOTHESIS AND OBJECTIVES

This pilot study aims to assess the feasibility and effects of a Virtual Reality Cognitive Training (VRCT) program on the cognitive function of older adults with Mild Cognitive Impairment (MCI).

2.1 Primary Objectives

Our primary objective is to (1): assess the retention and adherence rates of the VRCT intervention and (2) examine effects of VRCT on cognition, everyday memory performance and mood of older adults with MCI.

2.2 Potential Risks and Benefits:

2.2.1 Potential Risks

The use of VR equipment for an extended period of time may induce a dizzy feeling in older adults. In order to prevent this, we limit the duration of VR usage to under 30 minutes. We will also check in with our participants in regular intervals to assess their comfort levels. Participants with severe visual or hearing impairment will be excluded from this study.

2.2.2 Potential Benefits

Participants are expected to report improvements in cognitive functioning and mood after the program.

3 STUDY POPULATION

3.1 List The Number and Nature of Subjects to be Enrolled

As this is a pilot study, there is no power calculation for the sample. Based on the funding available, we intend to recruit up to 30 participants.

3.2 Criteria for Recruitment and Recruitment Process

The participants will be recruited from outpatient clinics in Changi General Hospital, referred by geriatricians and psycho-geriatricians.

3.3 Inclusion Criteria

- Aged 65-85
- Diagnosis of MCI by a clinician in accordance to Petersen's criteria
- Ability to see and hear
- Ability to read and write in either English or Mandarin
- Mini-Mental Status Examination > 23

3.4 Exclusion Criteria

- A primary other neurocognitive disorder
- Major psychiatric illness such as major depressive disorder or anxiety disorder
- Severe visual or auditory impairment
- Serious medical illnesses including acute or severe asthma, severe or unstable cardiovascular disease, active gastric ulcer, severe liver disease or severe renal disease

3.5 Subject Replacement

Participants who complete at least 8/10 sessions of VRCT will be included in the study. Dropouts will not be replaced.

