4.2.2 Study Visits and Procedures

For Virtual Reality Cognitive Training Intervention Group:

- Visit 1 (Week 1): Pre-intervention neuropsychological testing (2 hours)
- Visit 2-11 (Weeks 2-11): Virtual Reality Cognitive Training (50 minutes per session)
- Final Visit (Week 12): Post-intervention neuropsychological testing (2 hours)

For Active Control Group:

- Visit 1 (Week 1): Pre-intervention neuropsychological testing (2 hours)
- Visit 2 & 3 (5 weeks apart): Psychoeducation and Cognitive Stimulation (1 hour per session)
- Final Visit (Week 12): Post-intervention neuropsychological testing (2 hours)

During the VR session and cognitive training, frequent checks will be performed to ensure that subject is comfortable. Should subject express fatigue or discomfort, session can be stopped and resume when subject is able to continue. The number of breaks will be recorded.

Appointment between sessions will be at least 7 days apart.

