4.3 Discontinuation/Withdrawal

4.3.1 Discontinuation Criteria

The study will be discontinued for participants who continuously complain of discomfort and dizziness in using the Virtual Reality equipment.

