9.2 Statistical and Analytical Plans

Intention-to-treat analyses will be performed using the last observation carried forward method for subjects who were lost to follow-up or had missing data. Data will be analysed using IBM SPSS Statistics 26.0. Continuous variables will be presented as mean and standard deviation (SD) or median and interquartile range (IQR) where appropriate, while categorical variables will be presented as frequencies and percentages. A one-way analysis of variance will be conducted to assess the between-group difference of the intervention's effect over time for each outcome measurement. The significance level will be established at $p < 0.05$. Cohen's d effect size (ES) will be reported alongside the p-values, and thresholds of 0.2 for small, 0.5 for moderate, and 0.8 for large effects were employed as guiding benchmarks.

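### Section 3.5 ties inclusion in the study to attending 8 of 10 VRCT sessions, against the intention-to-treat plan in 9.2; used as the VRCT analysis set, it would fix completion at 100%

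*Combined protocol and SAP*

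**What the plan says.** Section 3.5 (Subject Replacement) consists of two sentences: "Participants who complete at least 8/10 sessions of VRCT will be included in the study" and "Dropouts will not be replaced".

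Section 9.2 sets the analysis principle: "Intention-to-treat analyses will be performed using the last observation carried forward method for subjects who were lost to follow-up or had missing data". It names no per-protocol or completer set and does not mention the 8/10 threshold.

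Section 2.1 makes it primary objective (1) to "assess the retention and adherence rates of the VRCT intervention". No section defines either rate or gives its denominator.

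Three other places bear on the point. Section 2.2.1 warns that "The use of VR equipment for an extended period of time may induce a dizzy feeling in older adults". Section 4.3.1 states: "The study will be discontinued for participants who continuously complain of discomfort and dizziness in using the Virtual Reality equipment". Section 7.3 gives 15 intervention subjects and a termination count of 8 or more who fail a completion end-point that is not defined.

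**The concern.** Attendance is known only after randomisation, so the 3.5 sentence cannot be an eligibility criterion; those are in 3.3 and 3.4 and do not mention sessions. As worded, it selects participants on a post-randomisation event in one arm. Section 9.2 does the opposite: carrying the last observation forward makes sense only if people who leave early stay in the analysis.

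Two things are at stake. The first is feasibility, which is half of the primary objective. An adherence rate computed among people chosen for attending says little about adherence. Those most likely to be missing are those who could not tolerate the headset, and the protocol intends the study to help "in guiding us to conduct a randomized controlled trial for a VRCT group program". The second is the efficacy comparison: if 3.5 were applied, a filtered VRCT arm would be set against an unfiltered control arm and the protection of randomisation would be lost.

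The discontinuation rule in 4.3.1 is not questioned. The issue is only whether the people it affects remain in the counts.

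**Working it through.** **Inputs**
- VRCT arm: 15 (section 7.3). This agrees with half of the planned maximum of 30 in 9.1: 30/2 = 15.
- Sessions per VRCT participant: 10 (4.2.2), so 15 × 10 = 150 scheduled sessions.
- Threshold: 8 of 10 (3.5). Completers attend 8 to 10 sessions, non-completers 0 to 7.
- Number below the threshold, k: not in the documents, so assumed. The top value, 7, is the largest below the termination count in 7.3 if completion there means 8/10, which the protocol does not say.
- Adherence is taken as sessions attended divided by sessions scheduled. This too is an assumption.

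The plan gives no retention, completion or adherence figure to reproduce.

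**Formulas, over all 15**
- Completion = (15 − k)/15
- Lowest adherence = 8(15 − k)/150
- Highest adherence = [10(15 − k) + 7k]/150

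**Results**

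| k | Completion, all 15 | Adherence, all 15 | Completion, 3.5 set | Adherence, 3.5 set | Analysed under 9.2 | Analysed with 3.5 on the VRCT arm |
|---|---|---|---|---|---|---|
| 0 | 15/15 = 100% | 120/150 = 80% to 150/150 = 100% | 15/15 = 100% | 80% to 100% | 15 + 15 = 30 | 15 + 15 = 30 |
| 1 | 14/15 = 93.3% | 112/150 = 74.7% to 147/150 = 98% | 14/14 = 100% | 80% to 100% | 30 | 14 + 15 = 29 |
| 3 | 12/15 = 80% | 96/150 = 64% to 141/150 = 94% | 12/12 = 100% | 80% to 100% | 30 | 12 + 15 = 27 |
| 7 | 8/15 = 53.3% | 64/150 = 42.7% to 129/150 = 86% | 8/8 = 100% | 80% to 100% | 30 | 8 + 15 = 23 |

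The last two columns assume that 30 are recruited, 15 per arm.

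**Same participants, two denominators.** The adherence ranges overlap because they span different attendance patterns. For any one set of participants, the 3.5 figure exceeds the all-15 figure by (k/15) × (completer mean − non-completer mean)/10. The difference in means lies between 8 − 7 = 1 and 10 − 0 = 10 sessions. The excess is therefore 0.7 to 6.7 percentage points at k = 1, 2 to 20 at k = 3, and 4.7 to 46.7 at k = 7. At k = 0 it is nil.

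**Retention.** Sessions start in Week 2 and are at least 7 days apart (4.2.2), so the eighth falls in Week 2 + 7 = Week 9 at the earliest. Post-intervention testing is in Week 12. The 3.5 set has therefore stayed to at least Week 9, but its Week-12 retention can still be below 100%.

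**Tolerability.** If 1 to 3 of the 15 (assumed) were discontinued for VR discomfort before session 8, that is 1/15 = 6.7% to 3/15 = 20% of those randomised to VRCT, and 0% of the 3.5 set.

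**The case against.** The best defence is that 3.5 was never meant to define an analysis set. It sits under a heading about replacement and speaks of the study, not the analysis; it may simply be a badly worded completer definition. Section 9.2 is the only stated analysis population and would ordinarily govern. Section 7.3 counts failures among all 15, and 4.3.2 collects feedback from people who withdraw; both suggest that non-completers are kept. Most of this stands, and it is why the harm is conditional. But no section says it, and 9.2 speaks of outcome measurements, so even on this reading the denominator for retention and adherence is left open.

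A reader might infer more than the documents support:
- *That 3.5 removes every control, since controls attend no VRCT sessions.* The literal wording does that, but section 16 reports a comparison with the control group, so the sentence was evidently not applied that way.
- *That retention is also 100% by construction.* The rule fixes completion, not attendance at Week 12.
- *That 7.3 contradicts 3.5.* It can operate as a monitoring count whatever set is analysed.
- *That the reported results come from completers only.* Section 16 does not say, and its Table 3 is not in the available text and may show who was analysed.

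It is also fair to say that every non-completer count here is assumed, and that with one non-completer the effect on adherence could be under one percentage point.

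**Conclusion.** The point holds as a conflict between 3.5 and 9.2 that the protocol does not resolve. It goes beyond missing detail, because following 3.5 as written for the VRCT arm gives a completion rate that cannot vary and an adherence rate that cannot fall below 80%. At the assumed 3 and 7 non-completers, completion is overstated by 20 and 46.7 percentage points; with none, the two readings agree.

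Confidence is high that the sections conflict and that no denominator is stated. It is not known whether 3.5 was used. If it was, the efficacy comparison is open to bias whose direction and size cannot be judged from the documents. If 9.2 governed, that comparison is unaffected and only the feasibility rates need attention.

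**What to change.** Replace the inclusion sentence in 3.5 with: *All randomised participants are analysed in the group to which they were randomised; completing at least 8/10 VRCT sessions is an adherence label and does not affect inclusion.*

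In 9.2, state that retention and adherence are computed over all participants randomised to VRCT, and label any completers-only analysis as a per-protocol sensitivity analysis. Report the number meeting 8/10, sessions attended out of 10, the number discontinued under 4.3.1 and Week-12 retention on that denominator.

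Because results already exist, rewording alone cannot act prospectively. State which participants the section 16 results cover, and add the all-randomised analysis only if completers alone were used.

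The cost is one sentence in 3.5, a stated denominator in 9.2 and a statement of who was analysed, with a further analysis only in that one case. The downside for the sponsor is that reported completion and adherence may be less favourable.

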4 STUDY DESIGN

This is a pilot feasibility study using a parallel design where participants are randomized into either the Virtual Reality Cognitive Training (VRCT) intervention group or the active control group. Study recruitment would be completed in approximately 3 months. Participants are expected to be involved in the study for no more than 12 weeks each.

4.1 Randomisation and Blinding

A biostatistician, independent of our research, will generate the random allocation sequence. Sealed envelopes will be used to conceal the random allocation sequence. Researchers will enrol the eligible participants and assign them to either the intervention or control group by following the sequence allocation. A Clinical Research Co-ordinator who is blinded to the group assignments will be conducting the outcome measures.

4.2 Study Visits and Procedures

4.2.1 Screening Visits and Procedures

All patients who have received a diagnosis of MCI and achieved a cognitive screening score of MMSE > 23 will be informed about the research by their primary physician when they attend their regular outpatient clinic visits. If patients were to express interest, the treating physicians will then seek patients' consent to be referred to the study team. Upon receiving the referral, researchers will then obtain permission from the primary physician to contact these patients about the purpose, procedures, risks and benefits of the study. If patients were to endorse their agreement over the phone, an invitation

letter will be mailed to potential participants to come to the hospital for consent-taking as well as undergo pre-intervention neuropsychological testing.

4.2.2 Study Visits and Procedures

For Virtual Reality Cognitive Training Intervention Group:

- Visit 1 (Week 1): Pre-intervention neuropsychological testing (2 hours)
- Visit 2-11 (Weeks 2-11): Virtual Reality Cognitive Training (50 minutes per session)
- Final Visit (Week 12): Post-intervention neuropsychological testing (2 hours)

For Active Control Group:

- Visit 1 (Week 1): Pre-intervention neuropsychological testing (2 hours)
- Visit 2 & 3 (5 weeks apart): Psychoeducation and Cognitive Stimulation (1 hour per session)
- Final Visit (Week 12): Post-intervention neuropsychological testing (2 hours)

During the VR session and cognitive training, frequent checks will be performed to ensure that subject is comfortable. Should subject express fatigue or discomfort, session can be stopped and resume when subject is able to continue. The number of breaks will be recorded.

Appointment between sessions will be at least 7 days apart.

